2.4.5.3 Deaths

The following deaths summaries will be generated on the safety population:

- Number (%) of patients who died by study period (pre-treatment, on-study, on-treatment, post-study) and reasons for death summarized by treatment arm,
- Death in non-randomized patients or randomized and not treated patients,
- TEAE leading to death (death as an outcome on the AE CRF page as reported by the Investigator) by primary SOC, HLG, HLT and PT showing number (%) of patients sorted by internationally agreed order of SOC and alphabetic order of HLG, HLT, and PT presented in alphabetic order within SOC.
- All pre-treatment AEs leading to death by primary SOC and PT, showing the number (%) of patients, sorted by the internationally agreed SOC order and decreasing incidence of PTs within each SOC (if more than 5 patient with the event),
- All post -treatment AEs leading to death by primary SOC and PT, showing the number (%) of patients, sorted by the internationally agreed SOC order and decreasing incidence of PTs within each SOC (if more than 5 patient with the event).

A listing of all deaths sorted by treatment arm will be performed.

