2.1.4.4 Deaths

The death observations are per the observation periods defined above. In addition, after the post-treatment period, death related to IMP as well as death resulting from TEAE must be reported to the Sponsor.

- Death on-study: deaths occurring during the on-study observation period (defined as the time from the signed informed consent date up to the end of the study, ie, last protocol planned visit or the resolution/stabilization of all SAE),
- Death pre-treatment: deaths occurring before the on-study observation period,
- Death on-treatment: deaths occurring during the on-treatment period,
- Death post study: death occurring after the end of study.

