2.3.2 Safety population

The safety population is defined as: all randomized patients who actually received at least one dose or part of a dose of IMP, analyzed according to the treatment actually received.

In addition:

- Non-randomized but treated patients will not be part of the safety population. This is a post marketing real world trial with commercially available insulin so that non-randomized but treated patients are not considered part of the trial and safety data are listed separately.
- Randomized patients for whom it is unclear whether they took the study medication will be included in the safety population as randomized.
- For any patient receiving more than one study treatment (Toujeo or “standard of care” basal insulin) during the trial, the patient will be analyzed in the treatment arm in which he/she was treated longer by either IMP (allocated by IRT or prescribed/dispensed) or Commercial basal insulin prescribed following a switch during the 6-month on-treatment period. This actual treatment arm, defined at time of 6-month database lock on the 6-month on-treatment period, will be applied at time of 12-month database lock (ie, to the 12-month on-treatment period).

If a patient is randomized more than once, only the data associated with the first randomization are used in the analysis population. The subject will be analyzed according to the first randomization treatment arm. All data collected after the second randomization will be excluded from the primary efficacy analysis. The safety experience associated with any later randomization is described separately.

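### The SAP puts its death summaries on a dosed population that cannot contain the untreated deaths listed under it, and defines pre-treatment death so that the row is always empty

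*SAP*

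**What the plan says.** SAP 2.4.5.3 opens with one population for the whole list: "The following deaths summaries will be generated on the safety population". The first item is the by-period table: "Number (%) of patients who died by study period (pre-treatment, on-study, on-treatment, post-study) and reasons for death summarized by treatment arm". The second item is "Death in non-randomized patients or randomized and not treated patients". Three tables of adverse events leading to death follow (treatment-emergent, pre-treatment, post-treatment). The section closes with "A listing of all deaths sorted by treatment arm will be performed".

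SAP 2.3.2 defines the safety population as "all randomized patients who actually received at least one dose or part of a dose of IMP", analyzed by treatment actually received. It makes one exception to the dosing condition: "Randomized patients for whom it is unclear whether they took the study medication will be included in the safety population as randomized". People treated without randomization are excluded.

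SAP 2.1.4.4 gives the death categories. On-study death uses a period "defined as the time from the signed informed consent date up to the end of the study". The next category is "Death pre-treatment: deaths occurring before the on-study observation period". SAP 2.1.4, to which 2.1.4.4 refers for its periods, differs on both terms: its on-study period begins at randomization, and its pre-treatment period runs from consent to the first injection. Protocol 9.2.3.4 starts on-study death at consent and has no pre-treatment death category; the SAP added one.

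**The concern.** There are two separate faults. First, the population named in the lead-in of SAP 2.4.5.3 excludes the people named in its second item. A programmer must either disregard the lead-in for that item or produce an empty output. Under the same rule, a randomized patient known never to have dosed who dies is missing from the only planned by-arm count of all deaths. Second, the death categories conflict: the on-study period has two start dates within one SAP, and pre-treatment death is defined as preceding a period that already begins at consent.

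Untreated patients are an expected group. SAP 2.2 counts randomized but untreated patients and SAP 2.2.1 lists them. US patients leave Visit 2 with a prescription and collect insulin from a pharmacy (Protocol 8.4 and 10.1.1.2), so randomization and first dose can be separated. Efficacy is analyzed on all randomized patients as randomized (SAP 2.3.1), but no death table on that basis would stand beside it. The by-period table follows actual treatment, with anyone who received both treatments placed in the arm in which they were treated longer.

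**Working it through.** No arithmetic applies; the plan states no figure for deaths or for untreated patients. The check crosses each possible time of death with the population rule (SAP 2.3.2) and the two sets of period definitions (SAP 2.1.4.4 and 2.1.4).

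| Time of death | Label under SAP 2.1.4.4 | Position under the SAP 2.1.4 periods | In the by-period table? | Where reported |
|---|---|---|---|---|
| Before consent | Pre-treatment | Outside every period | No, not a trial patient | Nowhere |
| Consent to randomization | On-study | Pre-treatment, before on-study | No, not randomized | Second item; listing |
| After randomization, known never dosed | On-study | Pre-treatment and on-study at once | No, no dose | Second item; listing |
| After randomization, dosing unclear | On-study | Depends on how first dose is handled | Yes, by the exception | By-period table; listing |
| After first dose | On-study, and on-treatment if within that window | Same | Yes | By-period table; listing |

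Four results follow.

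1. The second item of SAP 2.4.5.3 concerns rows two and three of this grid. Neither group is in the safety population, so the lead-in cannot govern that item.

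2. The pre-treatment row of the by-period table is zero whatever happens. With on-study starting at consent, it would need a death before consent. With on-study starting at randomization, it would need a death before randomization, and the safety population contains only randomized patients. If the row is read as consent to first injection, a patient with a confirmed dose cannot have died before it. For a patient in the population with unclear dosing, SAP 2.5.3 treats adverse events from randomization onward as treatment-emergent when the first administration date is missing.

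3. The population rule alone removes untreated deaths from the table. The definition in SAP 2.1.4.4 does not remove them; it would label them on-study. The definition therefore mislabels, and the population rule excludes.

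4. Correcting the definition alone would not fill the row, because the dosed population would still exclude the deaths. Both parts must change.

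**The case against.** The strongest reply is that these deaths are reported. The second item of SAP 2.4.5.3 names exactly this group, the listing covers all deaths, and SAP 2.4.5 says safety results are presented by treatment group. A reader might infer that untreated deaths disappear, or surface only in a listing. The documents do not support that. What remains is that the second item sits under a population that excludes its subjects, pools people never randomized with randomized patients who never dosed, and states no denominator. It does not replace a by-arm count on all randomized patients.

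A reader might also infer that every pre-treatment display is impossible on dosed patients. That goes too far. SAP 2.1.4.2 classifies an adverse event by when it developed, worsened or became serious, not by when the patient died. A patient whose event was already present before the first injection can be dosed, die of it later, and be in the safety population. The table of pre-treatment adverse events leading to death is therefore not necessarily empty.

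Nor is every patient without a confirmed dose excluded, since those with unclear dosing are kept. With US insulin coming from pharmacies and no treatment log at US sites (Protocol 8.8), that is a realistic group.

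Finally, showing dosed patients in one table and untreated deaths in another is a coherent choice, safety analysis here is essentially descriptive, and mortality is not a study objective. That limits the importance of the point. It does not reconcile the lead-in with its own list or the two start dates with each other.

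**Conclusion.** The point holds as an inconsistency in population and definitions. Followed literally, SAP 2.4.5.3 and 2.1.4.4 give a pre-treatment row that is zero by construction, a second item that cannot be produced on its stated population, and no death count by randomized arm on all randomized patients.

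Its size cannot be put as a number of deaths. The documents give neither the share of patients expected never to dose nor a mortality rate, and any count would rest wholly on assumed values. The conclusion needs no such assumption; it follows from the wording of the sections. It applies to patients known to be untreated, not to those with unclear dosing. The effect is confined to descriptive safety tables, and the primary analysis is unaffected.

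**What to change.** In SAP 2.4.5.3:

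- State the population for each death summary in place of a single lead-in.
- Present deaths by period on all randomized patients, as randomized, with never-treated patients as their own row. Keep the safety-population table as a second display.
- Take the second item out from under the safety-population lead-in, and report deaths in screened, non-randomized people separately from deaths in randomized, untreated patients.

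In SAP 2.1.4.4 and 2.1.4:

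- Define pre-treatment death as running from consent to first IMP, as the pre-treatment period of SAP 2.1.4 already does.
- Use one start date for the on-study period in both sections. Consent would match Protocol 9.2.3.4.

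One detail needs a sentence in the SAP. A randomized patient who dies before a first dose is by definition never treated, so the pre-treatment and never-treated rows overlap. The SAP should say in which of the two each such death is counted.

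The cost is SAP wording and one additional descriptive table. Adverse events are already collected from consent and deaths are already recorded, so no new data are needed.

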2.4.5.4 Analyses of laboratory safety variables

Not applicable.

2.4.5.5 Analyses of vital sign variables

The summary statistics (including number, mean, median, SD, minimum and maximum) of blood pressure, heart rate and body weight (values and changes from baseline) will be calculated for each visit or study assessment (baseline, each post baseline time point, last on-treatment) by treatment arm.

2.4.5.6 Analyses of electrocardiogram variables

Not applicable.

2.4.5.7 Analyses of Patient-Support Program (PSP)

Participation to a PSP will be described by visit and overall per randomized treatment arm on the safety population.

Furthermore, the number and percentage of patients having or not initiated a Toujeo PSP at any time during respectively the 6-month randomized period at time of 6 month database lock and the 12-month randomized period at time of 12 month database lock will be described in the Toujeo randomized treatment arm, according to demographic and baseline characteristics.

2.4.6 Analyses of pharmacokinetic and pharmacodynamic variables

Not applicable.

2.4.7 Analyses of patient reported outcome variables

The patient report outcomes (PRO) analyses will be performed on the ITT population.

Self-reported treatment satisfaction

DTSQs and DTSQc scores at 6 and 12 months will be compared between treatment groups using an ANCOVA approach as described for the continuous efficacy variables. The ANCOVA model with satisfaction score as the dependent variable includes HbA1c target and other stratification factors used at randomization: SU use (y/n), GLP-1 RA use (y/n) and baseline HbA1c (as continuous) in the model.

The consistency between results of DTSQs change from baseline to 12 months and DTSQc scores at 12 months will be assessed.

Cumulative distribution function of score changes from baseline at 6 and 12-months will be plotted by treatment arm for each of the 3 DTSQs scores. Cumulative distribution function of 12-month DTSQc scores will be plotted by treatment arm.

Hypoglycemia Patient Questionnaire

Items of the Hypoglycemia Patient Questionnaire will be summarized by descriptive statistics. a graphical presentation will also be provided.

The proportion of patients reporting one or more episodes of either moderate or severe hypoglycemia will be compared between treatment groups using the same logistic regression model as for GES detailed in following paragraph.

Global Effectiveness Scale

At each study endpoint, the proportion of patients and providers who reported “complete control of diabetes” or “marked improvement of diabetes” at 6 and 12 months will be analyzed using a logistic regression same as the primary efficacy analysis. The dependent variable is the “complete control/marked improvement” (y/n). The logistic model includes HbA1c target and other stratification factors used at randomization: SU use (y/n), GLP-1 RA use (y/n) and baseline HbA1c (as continuous) in the model.

Additionally, at each time point (6 months and 12 months), all response choices for both patients and provider will be summarized by descriptive statistics.

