11.4.4 Analyses of Patient Reported Outcomes

Self-reported patient satisfaction and hypoglycemia: Satisfaction scores at 6 and 12 months will be compared between treatment groups using a MMRM approach as described for the continuous efficacy variables. To adjust for the baseline differences between treatment groups, logistic regression will be conducted, adjusting for randomization strata of HbA1c target, SU use ever (y/n), GLP-1 RA use ever (y/n) and baseline A1c (as continuous).

Global Effectiveness Scale (GES): At each study endpoint, the proportion of patients and providers who reported “Excellent” or “Good” at 6 and 12 months will be analyzed using CMH tests adjusting for randomization strata.

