1.5 MODIFICATIONS TO THE STATISTICAL SECTION OF THE PROTOCOL

In the protocol (1) Section 11.4.2, Analyses of efficacy endpoints, defines the analysis of HbA1c endpoints (change from baseline to 6 months) and self-reported satisfaction score using a mixed-effect model with repeated measures (MMRM) approach under the missing at random (MAR) framework, using an adequate contrast at Month 6. Since at the time of the 6 month database lock, only baseline and 6 month HbA1c data are available, an analysis of covariance (ANCOVA) will be performed at time of 6 month database lock and a MMRM at time of 12 month database lock.

In the protocol (1) Section 11.4.2, Analysis of primary efficacy endpoint(s), exploratory analysis for primary endpoint was modified. The Predictive Enrichment method is replaced by Subgroup Identification Based on Difference Effect Search (SIDES). The rationale is that the predictive enrichment procedure does not adjust for multiplicity. Additionally, the definition of subgroups is based on a score, defined as a function of multiple covariates, which makes difficult the clinical interpretation. On the other side, SIDES method uses fewer covariates (ie, 2 or 3 covariates), that is easier to interpret from a clinical point of view. Additionally, SIDES corrects for multiplicity.

As mentioned in Clinical Trial Protocol Amendment No. 01, an IA is planned when 1800 patients have completed their 6 month visit. The calculation takes into account one IA using a group sequential approach with an efficacy boundary based on a gamma (-3) alpha spending function.

The cut-off date for the IA is the date when 1800 patients have completed their 6 month visit.

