2.4.4.2 Analyses of secondary efficacy endpoints

Change in HbA1c

The change in HbA1c from baseline to 6 months will be analyzed using an analysis covariance (ANCOVA) model. The model will include a fixed categorical effect of treatment arm, HbA1c target and other randomization strata; SU use (y/n), GLP-1 RA use (y/n), as well as baseline BMI (as continuous) and baseline HbA1c (as continuous).

The change in HbA1c from baseline to 12 months will be analyzed a MMRM approach under the MAR framework, using an adequate contrast at Month 12. The model will include fixed categorical effects of treatment arm, visit, treatment-by-visit interaction, HbA1c target and other randomization strata; SU use (y/n), GLP-1 RA use (y/n), and baseline A1c (as continuous), as well as baseline HbA1c-by-visit interaction. Both 6 months and 12 months HbA1c data will be included in the MMRM model.

The analysis of HbA1c is based on patients in the ITT population. For those with missing HbA1c value at 6 months, the change in HbA1c will be missing. Therefore, those patients will not be included in the analysis.

As sensitivity analysis, the imputed HbA1c values at 6 months and 12 months described in [Section 2.4.4.1](#) will be used to repeat the change in HbA1c from baseline to 6 months and to

12 months analysis models. The estimates from the 100 fitted models will be combined to provide an overall estimate with corresponding CIs for the treatment differences in change from baseline in HbA1c to 6 months and 12 months.

Change in FPG and body weight

The change in FPG and body weight from baseline to 6 and 12 months will be analyzed in a similar fashion to the change in HbA1c.

Other binary endpoints

The proportion of patients with HbA1c <8% and <7% without documented symptomatic (BG \leq 70 mg/dL) or severe hypoglycemia at 6 months and of patients with HbA1c <8% and <7% at 6 months will also be analyzed by the same logistic regression model as for the primary efficacy analysis.

The proportion of patients with individualized HbA1c target attainment without documented symptomatic (BG \leq 70 mg/dL) or severe hypoglycemia at 12 months, and the proportion of patients with individualized HbA1c target attainment without documented symptomatic (BG <54 mg/dL) or severe hypoglycemia at 6 and 12 months be analyzed as described for the primary endpoint.

Health resource utilization

Detailed analysis methods for health resource utilization will be described in a separate analysis plan.

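### SAP 2.4.7 gives ANCOVA for DTSQs at 12 months, while SAP 1.5, Protocol 11.4.4 and the section it cross-refers to give MMRM, so the 12-month model is not determined

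*SAP*

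**What the plan says.** Protocol 11.4.4 states: "Satisfaction scores at 6 and 12 months will be compared between treatment groups using a MMRM approach as described for the continuous efficacy variables".

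SAP 1.5, which declares departures from the protocol's statistical section, recalls that the protocol analyses HbA1c change and the "self-reported satisfaction score using a mixed-effect model with repeated measures (MMRM) approach under the missing at random (MAR) framework". Because only baseline and Month 6 HbA1c values exist at the first of these locks, it then provides that "an analysis of covariance (ANCOVA) will be performed at time of 6 month database lock and a MMRM at time of 12 month database lock". SAP 1.6 lists no further modification.

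On DTSQs and DTSQc, SAP 2.4.7 says: "scores at 6 and 12 months will be compared between treatment groups using an ANCOVA approach as described for the continuous efficacy variables". Besides HbA1c target, its covariates are "SU use (y/n), GLP-1 RA use (y/n) and baseline HbA1c (as continuous) in the model". It lists no visit term, no treatment-by-visit term and no baseline DTSQs score.

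SAP 2.4.4.2, where the continuous efficacy variables are described, uses ANCOVA for HbA1c change at 6 months and, at 12 months, an MMRM that takes in both the Month 6 and the Month 12 values.

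**The concern.** Two programmers following this SAP in good faith could fit different 12-month models to the same DTSQs data. The reason SAP 1.5 gives for ANCOVA, that only one post-baseline value is available, no longer holds at 12 months, because DTSQs is also collected at Month 6.

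The choice matters for patients who give a Month 6 score and then leave. ANCOVA on Month 12 scores drops them. MMRM keeps their Month 6 score and, if dropout is missing at random given that score, corrects for it. In an open-label trial it is plausible, though not shown, that dissatisfied patients leave more readily in one arm than in the other. At stake is the 12-month DTSQs comparison. Treatment satisfaction is part of a secondary objective, and the protocol's rationale says it interests payers.

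**Working it through.** **1. The sections side by side**

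| Place | 6 months | 12 months |
|---|---|---|
| Protocol 11.4.4, satisfaction scores | MMRM | MMRM |
| SAP 1.5, HbA1c and satisfaction score | ANCOVA | MMRM |
| SAP 2.4.7, DTSQs and DTSQc | ANCOVA | ANCOVA |
| SAP 2.4.4.2, HbA1c (the target of the cross-reference) | ANCOVA | MMRM, both visits |
| SAP 2.5.1, patient-reported effect sizes | LS means from MMRM or ANCOVA | same |

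SAP 2.4.7 therefore disagrees with SAP 1.5 and with its own cross-reference. No section declares a move to ANCOVA at 12 months.

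**2. Which scores are affected.** DTSQs is collected at Screening, Day 1, Month 6 and Month 12 (SAP 2.1.7.1), so an MMRM is feasible. DTSQc is collected at Month 12 only (SAP 2.1.7.2), so an MMRM has nothing to add there.

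**3. What happens to a patient with no Month 12 DTSQs.** The DTSQ missing-data rule is at item level: at least 4 of 6 items for the total score (SAP 2.5.1, Table 6). The multiple imputation in SAP 2.4.4.1 covers HbA1c and hypoglycemia only. Under a literal reading of 2.4.7 the patient leaves the 12-month comparison.

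**4. Size.** The documents give no SD, correlation or dropout rate for DTSQs, so there is no stated figure to reproduce. Assumed inputs:

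- SD σ = 6 for the total score.
- Correlations: Month 6 with Month 12, ρ = 0.65; baseline with Month 6, 0.45; baseline with Month 12, 0.40.
- Dropout after Month 6 of 10% or 20% in each arm.
- In one arm the log-odds of dropout fall by 0.7 per SD of Month 6 score; in the other there is no dependence.
- 1662 per arm (the planned number).

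Let m be the mean standardised Month 6 score of those who stay in the affected arm. Numerical integration of the logistic dropout model over a standard normal score gives m = 0.0668 at 10% and 0.1299 at 20%.

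- Covariates as listed in 2.4.7 (no baseline score), bias = σ × ρ × m: 6 × 0.65 × 0.0668 = 0.26 points; 6 × 0.65 × 0.1299 = 0.51 points.
- Baseline DTSQs added, ρ replaced by 0.65 − 0.45 × 0.40 = 0.47: 6 × 0.47 × 0.0668 = 0.19; 6 × 0.47 × 0.1299 = 0.37.
- Milder imbalance (0.7 in one arm, 0.35 in the other, for which m = 0.0346 and 0.0687; no baseline score): 3.9 × (0.0668 − 0.0346) = 0.13; 3.9 × (0.1299 − 0.0687) = 0.24.
- Equal dependence in both arms: m is the same in each arm and the bias cancels.

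The bias favours the arm in which dissatisfied patients leave.

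**5. Check by simulation.** 300 trials per setting, 1662 per arm, true difference 1 point, SD 6, between-visit correlation 0.4 or 0.6, dropout risk 10% or 20% at the average score, no baseline score in the model, Monte Carlo standard error about 0.013:

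| Dropout after Month 6 | ANCOVA bias | MMRM-equivalent bias |
|---|---|---|
| Completely random | −0.02 to +0.01 | −0.02 to +0.01 |
| Depends on Month 6 score equally in both arms | −0.01 to −0.04 | −0.01 to +0.01 |
| Depends on Month 6 score in one arm only (1.0 per SD) | −0.26 to −0.74 | −0.01 to +0.03 |

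**6. Scale.** On the effect-size scale of SAP 2.5.1, 0.26/6 = 0.04, 0.51/6 = 0.08 and 0.74/6 = 0.12, all below the 0.2 under which the SAP calls an effect negligible. Against sampling error they are not negligible. The standard error is 6 × √(2/(1662 × 0.9)) = 0.22 at 10% dropout and 6 × √(2/(1662 × 0.8)) = 0.23 at 20%, so the step 4 biases without a baseline score are about 1.2 and 2.2 standard errors.

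**7. Precision.** Under random dropout of fraction d, the variance ratio of MMRM to completer ANCOVA (no baseline score) is 1 − ρ²d. The standard-error ratio is √(1 − 0.4225 × 0.10) = 0.98 or √(1 − 0.4225 × 0.20) = 0.96, so completer ANCOVA gives up about 2% to 4%.

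**The case against.** The best defence is that this is loose drafting. The cross-reference in 2.4.7 leads to a section that uses MMRM at 12 months, SAP 1.5 names the satisfaction score explicitly, SAP 2.5.1 still expects an MMRM for patient-reported outcomes, and the protocol says MMRM. The weight of the text favours MMRM. That stands, and a reader who infers that the SAP deliberately chose a biased estimator goes beyond the documents. It does not remove the defect: 2.4.7 is the section that specifies the analysis, and it says ANCOVA at both times.

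A reader might also infer that the 12-month comparison will be biased, or will have an inflated false-positive rate. The documents do not support that. Every input to the bias is assumed, nothing shows that dropout depends on satisfaction differently by arm, and equal dependence gives almost no bias. Patients who stop study insulin are encouraged to stay to Day 360 (Protocol 10.3.3), although required follow-up reaches only Day 180 (10.3.4). SAP 2.4.4.3 calls all secondary endpoints exploratory and descriptive, and Protocol 9.3 places patient-reported outcomes under other endpoints, so no confirmatory claim rests on a DTSQ p-value. MMRM itself protects only under missing at random.

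Two further extensions fail. The Month 6 argument does not reach DTSQc, which is measured once. And the covariate in the Month 6 HbA1c ANCOVA ("as well as baseline BMI (as continuous) and baseline HbA1c (as continuous") that appears in neither the protocol's model nor the 12-month MMRM is a separate, minor documentation point: no bias follows from adjusting for prespecified baseline BMI in a randomised comparison.

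**Conclusion.** The conflict is real and needs no assumption to establish: the SAP does not determine the 12-month DTSQs model. The consequence is conditional. A literal reading of 2.4.7 loses some precision. It biases the 12-month difference only if dropout after Month 6 depends on the Month 6 score differently by arm. With SD 6, 10% to 20% dropout and dependence in one arm only, that bias is roughly 0.2 to 0.5 points on a 0 to 36 scale. It grows with stronger dependence and is near zero when dependence is equal. The point concerns one exploratory patient-reported comparison and leaves the primary result untouched. It is worth correcting because the correction is simple and restores what SAP 1.5 already says.

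**What to change.** Reword SAP 2.4.7 to state:

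- DTSQs at the 6-month lock: ANCOVA.
- DTSQs at the 12-month lock: MMRM using the Month 6 and Month 12 scores, with visit and treatment-by-visit terms and a Month 12 contrast, as SAP 1.5 provides.
- DTSQc at 12 months: ANCOVA, without mention of a 6-month DTSQc score.
- Baseline DTSQs score as a covariate in these models. SAP 2.1.7.2 says DTSQs will serve to control for baseline, but the covariate list in 2.4.7 omits it.

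If ANCOVA for DTSQs at 12 months was intended, declare and justify it in SAP 1.5 as a change from the protocol, and remove the cross-reference to the continuous efficacy variables.

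The cost is SAP wording. No new data are needed, and the same kind of MMRM is already planned for HbA1c at 12 months.
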